
## 3.2 Study Endpoints

### 3.2.1 Primary Effectiveness Endpoint

- The primary effectiveness endpoint is the Rate of Complete Aneurysm Occlusion (RCAO) at 12 months post-procedure according to the Raymond Scale as assessed by the Independent Core Laboratory.

Complete aneurysm occlusion is defined as an aneurysm in which a score of 1 (complete obliteration) is achieved on the Raymond Scale at the relevant post-procedure angiogram, without additional procedures for treatment of the aneurysm since the index procedure. Subjects who are retreated (retreatment includes staged procedures) prior to the 12 month post-procedure follow-up visit will be considered not to have achieved complete aneurysm occlusion for the purpose of the primary endpoint analysis.

The primary endpoint analysis will be to demonstrate that the RCAO is significantly greater than a performance goal (PG) of 35%. The primary endpoint null and alternative hypotheses are:

Null hypothesis  $H_0$ :  $\text{RCAO} \leq 35\%$

Alternative hypothesis  $H_A$ :  $\text{RCAO} > 35\%$

This analysis will be conducted on the modified intent-to-treat (MITT) population of subjects (subjects who are found to be eligible for treatment with ENTEPRISE at the time of the pre-procedure angiographic assessment, and in whom treatment is attempted). A supportive analysis will be conducted on the PP population.

**Note:** The study will be deemed to be a success if this primary efficacy endpoint null hypothesis (on the MITT population with data from all sites combined) is rejected in favor of the alternative hypothesis.

### 3.2.2 Primary Safety Endpoints

There are two primary safety endpoints: the rate of Major Ipsilateral Stroke and/or Death at 12 months post-procedure and In-stent Stenosis at 12 months post-procedure.

The analyses of these safety endpoints will be conducted on the MITT population. Supportive analyses will be conducted on the PP population.

#### 3.2.2.1 Incidence of Major Ipsilateral Stroke and/or Death

The incidence of a major ipsilateral stroke and/or death will be evaluated from the start of the index procedure until completion of the 12 month follow-up. A major ipsilateral stroke is defined as a new neurological event which is ipsilateral and in the vascular distribution territory of the stenting procedure and that results in an increase of  $\geq 4$  on the National Institute of Health Stroke Scale (NIHSS) as compared to baseline and persists for greater than 24 hours.

For a successful evaluation of this endpoint, the upper confidence limit of a 2-sided 95% confidence interval for the proportion of subjects who experience major ipsilateral stroke and/or death through 12 months post-procedure will be less than 25%.

### **3.2.2.2 Incidence of In-Stent Stenosis**

The percentage of aneurysms in which in-stent stenosis is assessed angiographically, at or prior to 12 months post-procedure will be evaluated. In-stent stenosis is defined as greater than 50% narrowing of the vessel within the ENTERPRISE stent or within 10 mm of either end of the stent (i.e., in-stent stenosis).

For a successful evaluation of this endpoint, the upper confidence limit of a 2-sided 95% confidence interval for the rate of stenosis at or prior to 12 months post-procedure will be less than 15%.

### **3.2.3 Secondary Effectiveness Endpoints**

The following secondary effectiveness endpoints have been defined. Observed rates will be described for both the MITT and PP populations; All angiographic imaging results will be based upon assessments by the independent Core Laboratory. A subject who is retreated (retreatment includes staged procedures) is considered to be a treatment failure for endpoints based on angiographic imaging.

#### **3.2.3.1 Procedure Success Rate**

The procedure success rate is defined to be the percentage of aneurysms in which coil mass position is maintained within the sac with parent artery patency, without additional procedures for treatment of the aneurysm since the index procedure. The procedure success rate will be summarized immediately post-treatment (acute), and at the 6 and 12 month follow-up assessments.

#### **3.2.3.2 Complete Aneurysm Occlusion as per the Raymond Scale**

The percentage of aneurysms in which a score of 1 (complete obliteration) is achieved on the Raymond Scale immediately post-procedure (acute) and at the 6 and 12 month follow-up angiographic assessments, respectively, will be evaluated.

### **3.2.3.3 Complete/Partial Aneurysm Occlusion as per the Raymond Scale**

The percentage of aneurysms in which a score of 1 (complete obliteration) or 2 (residual neck) is achieved on the Raymond Scale immediately post-procedure (acute), and at the 6, and 12 month follow-up angiographic assessments will be evaluated.

### **3.2.3.4 Percent Aneurysm Occlusion**

The percentage of aneurysms with occlusion of 100%, 90%-99%, 70-89%, 50-69%, 25-49%, or <25% occlusion in accordance with Consensus Grades 0-5, respectively, will be summarized immediately post-procedure (acute), and at the 6 and 12 month follow-up, respectively.

### **3.2.3.5 Recanalization Rate**

The percentage of aneurysms in which recanalization is documented at any time up to and including the 12 month follow-up visit, will be evaluated. Recanalization will be defined as an increase in aneurysm filling as compared to the previous study-specified angiographic assessment, resulting in a change in (i.e., worsening of) the Raymond classification. Changes in Raymond Scale will be classified as stable, improved, or recanalized based on the follow-up angiograms. Percentages of aneurysms falling into each of the categories will be presented.

### **3.2.3.6 Retreatment Rate**

The percentage of target aneurysms that are retreated at any time up to and including the 12 month follow-up visit will be evaluated. Retreatment will be defined as any additional treatment of the target aneurysm after the index procedure (retreatment includes staged procedures), or an additional procedure (regardless of whether retreatment is by surgery or endovascular treatment) due to recanalization, rupture or bleeding.

## **3.2.4 Secondary Safety Endpoints**

The evaluation of the rate of new neurological deficits (increase in mRS > 2 from baseline not related to stroke or death) at 12 months will be a pre-specified, powered analysis. All other secondary endpoints will be presented as a group to better characterize the ENTERPRISE stenting procedure.

Unless otherwise stated, these secondary safety analyses will be conducted on the MITT population.

### **3.2.4.1 Rate of New Neurological Deficits as per the Modified Rankin Scale (mRS)**

Observed scores on the Modified Rankin Scale will be presented at baseline (pre-procedure) and follow-up (30 days, 6 and 12 months post-procedure). The number and percentage of subjects who have an increase in mRS > 2 from baseline not related to stroke or death will also be presented for each follow-up time point.

### **3.2.4.2 NIH Stroke Scale (NIHSS) Total Score**

The NIHSS Total Score evaluations will be summarized at baseline (pre-procedure) and follow-up (6 and 12 months post-procedure); change from baseline at 6 and 12 months will also be summarized. The percentage of subjects who show a worsening from baseline (increase of 4 points or more) will also be presented. Observed scores and change from baseline will also be presented for NIHSS excluding scores on the aphasia subscale.

### **3.2.4.3 Adverse Events and Clinical Complications**

Adverse Events (AEs), including complications associated with an untoward medical occurrence, from the start of the index procedure until completion of the 12 month follow-up will be coded using the MedDRA system and summarized with frequencies. Serious adverse events (SAEs), device- or procedure-related AEs, unanticipated adverse device effects (UADEs) and deaths will be presented.

AEs will be presented for the following study periods: 1) peri-procedure – i.e., from the start of the procedure until 24 hours post-procedure; and, 2) through 12 month follow-up – i.e., from 24 hours post-procedure through the 12 month visit or premature termination.

### **3.2.4.4 Reduced TICI Flow**

The percentage of target aneurysms in which a new occurrence of unintentional and persistent reduced TICI flow (TICI score of 0 or 1) is observed at the target vessel during the index procedure as a result of a mechanical obstruction such as dissection or luminal thrombus will be evaluated.

### **3.2.4.5 Bleeding Complications**

The number and percentage of subjects who experience a procedure-related hemorrhagic event which requires any of the following will be evaluated: blood transfusion, surgical intervention, a new hospitalization, or lengthening of hospital

stay. The complications of hematoma requiring treatment (i.e., a hematoma > 5 cm in diameter occurring at the access site) and retroperitoneal bleeding will be reported as hemorrhagic events.

#### **3.2.4.6 In-stent Stenosis (Acute, and 6 Months)**

The percentage of aneurysms in which in-stent stenosis is documented immediately post-procedure (acute), and up to and including 6 months post-procedure, will be evaluated.

Acute in-stent stenosis will be further characterized by whether it results from vasospasm, and whether or not the vasospasm was responsive to medication.

#### **3.2.4.7 Thrombosis**

The percentage of aneurysms in which thrombosis is documented up to and including 6 and 12 months post-procedure will be evaluated. Thrombosis is defined as in-stent thrombosis.

### **3.2.5 Ancillary Endpoint**

#### **3.2.5.1 Stent Movement/Migration**

Incidence of stent movement and/or migration from the start of the index procedure until completion of the 12 month follow-up

### **3.2.6 Safety Follow-up through 24 months post-procedure**

Subjects who experience any of the following AEs of Special Interest and who have an MRS > 2 at any clinical evaluation will be followed through 24 months post-procedure, and their outcomes will be summarized in a supplemental safety follow-up report:

- All adverse events
- Rupture of the index aneurysm beyond 24 hours post-treatment
- Major ipsilateral stroke more than 1 month post-treatment
- Ipsilateral parenchymal hemorrhage more than 1 month post-treatment

## **4.0 ELIGIBILITY OF SUBJECTS, EXCLUSIONS AND REMOVAL OF SUBJECTS**

Subjects eligible for initial study screening are subjects who present with unruptured wide-neck, intracranial, saccular anterior circulation aneurysms and who are judged to be candidates for stenting. Every effort will be made to establish eligibility of the participants prior to enrollment.

Subjects who agree to voluntarily sign a study informed consent will be considered "enrolled" in the study, and will comprise the subject populations for this study.

Enrolled subjects who meet all of the general inclusion criteria and none of the general exclusion criteria described in this protocol will proceed with confirmation of angiographic inclusion/exclusion criteria.

Pre-treatment angiography performed during the index procedure will be utilized for final assessment of angiographic eligibility criteria. Subjects, who meet all of the general and angiographic inclusion/exclusion criteria, including the requirement for only one aneurysm to be treated, may be treated with ENTERPRISE. Subjects will be “entered” in the study (if the intent is to proceed with stent deployment) at the time of the start of the index procedure as defined in this protocol (see definitions). All subjects entered will be evaluated, regardless of sequence of treatment that ensues.

Subjects who are enrolled but not entered due to angiographic ineligibility resulting from either a pre-procedure angiogram or a pre-treatment angiogram will be considered an Angiographic Screening Failure (ASF) and will be followed for the period 72 hours following the end of the angiogram, or until discharge, whichever comes first, or to resolution of any adverse event, whichever is longer, and then will be discontinued from the study.

All subjects “entered” in the study are considered follow-up eligible and will be required to adhere to the follow-up schedule outlined in this protocol. Subjects who withdrew consent after treatment will be followed until the time of their withdrawal. Subjects who receive a retreatment of the study aneurysm will be followed for safety until the completion of their 24 month follow-up or premature study termination. These aneurysms will not be assessed for effectiveness beyond the retreatment.

Subjects who were determined by the investigator to meet the angiographic eligibility criteria, and received treatment with ENTERPRISE, but upon core lab review do not meet these criteria will be included in the effectiveness analysis in the Modified Intent-to-Treat population. However, the subject will be excluded from the Per Protocol population.

## **4.1 Criteria for Eligibility**

### **4.1.1 General Inclusion Criteria**

Prior to entry in this study, candidates must meet ALL of the following criteria:

1. Subject is 21 to 70 years, inclusive.
2. Subject whose target aneurysm is an unruptured wide-neck, intracranial, saccular anterior circulation aneurysm ( $\leq 10$  mm) arising from a parent vessel with a diameter of  $\geq 2.5$  mm and  $\leq 4$  mm who is referred for endovascular treatment. Wide-necked is defined as width  $\geq 4$  mm or a dome-to-neck ratio  $< 2$ .
  - i. For aneurysms  $< 5$  mm, subject must have another factor that increases the risk of rupture, specifically:

1. Aneurysm is irregular in shape (e.g. multi—lobulated/with daughter sac)
2. Interval increase in aneurysm size
3. Subject with history of subarachnoid hemorrhage (non-target aneurysm)
4. Subject with 2 first degree relatives with history of aneurysmal SAH
3. Subject whose target aneurysm is located in the anterior circulation.
4. Subject understands the nature of the procedure and provides voluntary written informed consent prior to the treatment.
5. Subject is willing to comply with specified follow-up evaluation and is willing to return to the investigational site for the thirty day, 6 month and 12 month, 18 month and 24 month follow-up evaluations.

#### **4.1.2 General Exclusion Criteria**

Candidates must be excluded from this study if ANY of the following criteria are met:

1. A planned staged procedure (a staged procedure is a procedure where entire treatment with the device (e.g., coils/stents) is completed over separate sessions).
2. Currently enrolled in another investigational device or drug study that has not reached the primary endpoint or that clinically interferes with the current study endpoints.
3. Two or more aneurysms (> 2 mm) in associated distribution.
4. More than 2 aneurysms (> 2 mm) total, previously treated or untreated.
5. Target aneurysm that has been previously treated
6. A non-target intracranial aneurysm expected to require treatment during the 12 month follow-up period.
7. A previous neuro-interventional or neuro-surgical procedure of any kind within 30 days prior to the study procedure.
8. A ruptured aneurysm.
9. Mycotic, fusiform or dissecting aneurysm.
10. Arteriovenous malformation (AVM) in the territory of the target aneurysm.

11. A Barthel Index < 80 from baseline condition not secondary to index aneurysm.
12. An intracranial mass (tumor, abscess, or other infection).
13. Dementia.
14. Admission platelet <50,000 or any known hemorrhagic diathesis, coagulation deficiency, or on oral anticoagulant therapy with an INR >3.0
15. A serum creatinine level > 2.5 mg/dL within 14 days prior to index procedure which the investigator determines restricts the use of contrast agents.
16. Known hypersensitivity/allergies or contraindication to aspirin, bivalirudin, clopidogrel or ticlopidine, cobalt, nitinol metal, nickel, or sensitivity to contrast media, which cannot be adequately pre-medicated or subject unable/unwilling to undergo therapy.
17. Cannot receive heparin during the study procedure.
18. A previously implanted intracranial stent associated with the symptomatic distribution within the past 12 weeks.
19. A previously implanted carotid stent associated with the symptomatic distribution within the past 12 weeks.
20. Evidence of an acute myocardial infarction (MI) within 31 days of the intended study procedure.
21. Currently has uncontrolled atrial fibrillation or known cardiac disorders likely to be associated with cardioembolic symptoms.
22. Females who are currently pregnant or intend to become pregnant during the study.
23. Patients with ongoing treatment of cancer or any patient who does not have a 5 year life expectancy from congestive heart failure, renal failure or other significant medical problems.
24. A history of stroke, cerebrovascular accident or transient ischemic attack in the last 6 months.
25. Active peptic ulcer or active gastrointestinal (GI) bleeding.
26. Otherwise determined by the investigator to be medically unsuitable for participation in this study.

27. A prisoner.
28. Evidence of active infection (WBC  $>10 \times 10^9 /L$ )
29. Target aneurysm is an extradural aneurysm(s)
30. Current substance-abuse /illicit drug use

#### **4.1.3 Angiographic Inclusion Criteria**

Candidates must meet ALL of the following criteria:

1. An unruptured wide-neck, intracranial, saccular anterior circulation aneurysm (target aneurysm)
2. Aneurysm size is  $\leq 10$  mm.
  - i. For aneurysms  $< 5$  mm, subject must have another factor that increases the risk of rupture, specifically:
    1. Aneurysm is irregular in shape (e.g. multi—lobulated/with daughter sac)
    2. Interval increase in aneurysm size
    3. Subject with history of subarachnoid hemorrhage (non-target aneurysm)
    4. Subject with 2 first degree relatives with history of aneurysmal SAH
3. Target aneurysm for the study treatment arises from a parent vessel with a diameter of  $\geq 2.5$  mm and  $\leq 4$  mm.
4. A wide-necked aneurysm. Wide-necked is defined as width  $\geq 4$  mm or a dome-to-neck ratio  $< 2$ .

#### **4.1.4 Angiographic Exclusion Criteria**

Candidates must be excluded if ANY of the following criteria are met:

1. Angiogram demonstrates that the target aneurysm is not appropriate for endovascular treatment (i.e.: severe intracranial vessel tortuosity or stenosis, intracranial vasospasm not responsive to medical therapy).
2. Aneurysm is expected to require more than one stent.
3. Aneurysm will or may be treated with a Hydrocoil(s) (the use of all other polymer coils is not an exclusion criteria).

## **4.2 Early Withdrawal of Subjects**

### **4.2.1 Withdrawal Criteria**

A subject can stop his or her participation by withdrawing his/her consent or when he/she is no longer able to participate in the study. Withdrawing consent will not result in any penalty whatsoever for the subject. Further treatment will be performed according to local practice. In case of a device-related or procedural-related adverse event that occurred as a result of participating in this study, the subject will be treated according to local practice.

The data of the subject who withdraws his/her informed consent will not be discarded, and will be used in the final analysis of the study, unless the subject specifically requests that the data not be used.

If a subject decides to withdraw from the study, he/she may do so at any time. However, the reason for discontinuation must be recorded in the source documentation and on the CRF. Possible reasons for premature discontinuation may include, but are not limited to, the following:

- Subject decides to withdraw from the study
- Investigator decides to withdraw subject from the study
- Lost to follow-up: after three attempts to reach the subject by telephone have failed, a certified letter will be sent to the subject. The subject will be considered lost to follow-up if this communication is unsuccessful.

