Subjects entered into the study will be considered eligible for follow-up unless they have died or withdrawn their consent to be contacted. The study center will review the follow-up requirements with the subject to help ensure compliance with the follow-up schedule. Telephone numbers should be obtained from the subject to ensure the ability to contact him or her at the required follow-up times. These phone numbers should include all home numbers, work numbers and primary physician numbers. A phone number of a relative or friend should also be requested.

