### **MITT Analysis Set**

The MITT analysis set consists of all ITT subjects who meet all pre-procedure angiographic eligibility criteria, and in whom treatment with the Enterprise device is attempted.

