## **10.3 Management of Post-procedure Symptoms**

If clinical symptoms deteriorate, the subject must be seen and assessed by the study investigator immediately. This does not exclude the subject from the study and follow-up should continue. All subjects entered into the study remain in the study until the 24 month post procedure study follow-up visit has been reached.

If a subject presents with an adverse event at the 24 month study visit, he/she will receive appropriate treatment for that condition. If the subject's condition precludes him or her from undergoing any 24 month evaluation specified by the protocol, the subject would be discharged from the study after the Investigator documents in the subject's medical record that a stable clinical endpoint has been reached, or that the subject's status is not associated with the device or procedure.

Following the 24 month study visit, the subject will be discharged from the study. However, if at the 24 month study visit the investigator determines there are indications of delayed hydrocephalus or in-stent stenosis

occurring, additional follow-up may be required, including MRI or CT at the Investigator's discretion. If this occurs, the investigator will determine the additional follow-up required at that time and inform the study sponsor.

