10.1 General Conventions

According to the Close Out plan, only descriptive statistics and listings will be presented, no inferential statistics will be performed for the primary and secondary endpoint. Descriptive statistics for continuous variables will include the number of subjects, mean, standard deviation, median, minimum and maximum. Descriptive statistics for dichotomous/categorical variables will include the number and percentage of subjects. All summary tables will be presented overall. Unless specified otherwise, percentages are based on non-missing values, excluding missing data and subjects who early discontinued.

- Baseline

Baseline is defined as the last non-missing measurement prior to the index procedure.

- Study Day

Unless specified otherwise, Study Day will be calculated as the difference between the event date and the date of index procedure, i.e., event date - date of index procedure. The day of index procedure is considered as Day 0.

- Date conversion

For the purposes of statistical analyses, a month is considered equivalent to 30 days and a year is considered equivalent to 360 days.

- SAS version

All statistical analyses will be performed using SAS®, Version 9.2 or later, unless otherwise noted.

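### Protocol 4.2.1 lets a withdrawing subject have recorded outcomes left out of the analysis, neither document says how that subject is then counted, and the SAP's percentages also leave out early discontinuers

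*Protocol*

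**What the plan says.** **Removal on request.** Protocol 4.2.1 makes retention the default: a withdrawing subject's data are kept and "will be used in the final analysis of the study, unless the subject specifically requests that the data not be used". It sets no limit on when the request may be made. Neither document gives an analysis rule for a subject who makes it.

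**Withdrawal by the investigator.** The list of possible reasons in 4.2.1 includes "Investigator decides to withdraw subject from the study", without criteria, although "the reason for discontinuation must be recorded in the source documentation and on the CRF". Two other sections leave no room for this item. The closing paragraph of Protocol 6.3.8 reads: "Subjects entered into the study will be considered eligible for follow-up unless they have died or withdrawn their consent to be contacted". Protocol 10.3 reads: "All subjects entered into the study remain in the study until the 24 month post procedure study follow-up visit has been reached".

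**Who belongs to the analysis set.** Protocol 9.8 defines MITT as "all ITT subjects who meet all pre-procedure angiographic eligibility criteria, and in whom treatment with the Enterprise device is attempted". SAP 7 uses the same basis. Nothing that happens after attempted treatment removes a subject from the set.

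**Missing data.** Protocol 9.5 uses LOCF for the primary effectiveness and primary safety endpoints. It counts a treated subject with no post-procedure data as an effectiveness failure and excludes that subject from the other endpoint analyses. SAP 10.4.1.1 excludes a missing 12-month Raymond score, 10.4.1.2 excludes missing stenosis data, 10.6 imputes nothing unless stated otherwise, and 10.7 plans no sensitivity analysis. Unless specified otherwise, SAP 10.1 bases percentages on non-missing values, "excluding missing data and subjects who early discontinued".

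**The concern.** This is an open single-arm study, so subject and investigator may know the outcome when a withdrawal or a removal request is made. If the chance of leaving the analysis depends on that outcome, the rates computed on those who remain are biased. Should subjects with a bad result be the more likely to leave, stroke/death and stenosis would look too low and RCAO too high. The documents give no evidence on whether that happens. The plan allows it, however, and has no rule that would show it or put a bound on it. Once data are taken out on request, the true rate cannot be recovered from what is left.

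**Working it through.** **1. The plan's own figures.** Protocol 9.9 gives safety power at 150 evaluable subjects with the null proportion in the variance: power = Φ{(p0 − p1 − 1.96·√[p0(1 − p0)/n]) / √[p1(1 − p1)/n]}.
- Stroke/death (p0 = 25%, p1 = 14%): (0.11 − 0.0693)/0.02833 = 1.437, so 92.5%. Stated: 92.5%.
- Stenosis (p0 = 15%, p1 = 6%): (0.09 − 0.0571)/0.01939 = 1.694, so 95.5%. Stated: 95.5%.
- RCAO at the interim (goal 35%, two-sided p < 0.031, critical z = 2.157): 66/150 is the smallest passing count, and its exact probability at a true rate of 47% is 79.3%. Stated: 79.3%.

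No stated figure is in dispute. They are only the base for what follows.

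**2. How each kind of subject is counted.**

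| Treated subject | Protocol 9.5 | SAP |
|---|---|---|
| All post-procedure data removed on request | RCAO: can be read as a failure. Safety: excluded | RCAO and stenosis: excluded. Stroke/death: no rule of its own, so 10.1 excludes |
| Withdrawn by the investigator after a poor 6-month angiogram | 6-month result carried forward, so counted | No 12-month Raymond score, so excluded from RCAO |
| Stroke or stenosis recorded, then early discontinuation, data kept | Event carried forward, so counted | Read literally, 10.1 takes the subject out of the percentage; 10.4.1.2 states no exception |

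The Protocol gap therefore lies mainly in the safety endpoints. The SAP gap covers all three primary endpoints.

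**3. Direction.** If k subjects with an event leave, x/n becomes (x − k)/(n − k), which is smaller whenever x < n. If k occlusion failures leave, s/n becomes s/(n − k), which is larger.

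**4. Size in the descriptive results.** The documents give neither the final sample size nor the number of requests, so both are assumed here: n from 50 to 150, and one unfavourable subject lost. Starting rates are the Protocol's planning values.

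| Assumed n | Stenosis | Stroke/death | RCAO |
|---|---|---|---|
| 50 | 3/50 = 6.0% → 2/49 = 4.1% | 7/50 = 14.0% → 6/49 = 12.2% | 22/50 = 44.0% → 22/49 = 44.9% |
| 100 | 6/100 = 6.0% → 5/99 = 5.1% | 14/100 = 14.0% → 13/99 = 13.1% | 44/100 = 44.0% → 44/99 = 44.4% |
| 150 | 9/150 = 6.0% → 8/149 = 5.4% | 21/150 = 14.0% → 20/149 = 13.4% | 66/150 = 44.0% → 66/149 = 44.3% |

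The exact (Clopper-Pearson) upper limit, from the beta quantile at 0.975 with parameters x + 1 and n − x, moves with the rate: 3/50 gives 16.5% and 2/49 gives 14.0%.

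**5. Borderline illustration under the Protocol's testing rules.** Upper limit = p + 1.96·√[p(1 − p)/n].
- Stenosis, goal 15%: 16/150 gives 15.61% (missed); 15/149 gives 14.90% (met).
- Stroke/death, goal 25%: 29/150 gives 25.65% (missed); 28/149 gives 25.06% (missed); 27/148 gives 24.47% (met).
- RCAO: 65/150 gives z = 2.140 (not significant); 65/149 gives z = 2.207 (significant). If every removed subject is a failure, the exact chance of false interim success at a true rate of 35% rises from 1.40% with none removed to 2.11% with one, 3.11% with three, 6.29% with eight and 8.64% with eleven (about 7% of 150).

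**The case against.** Much of the other side's case stands.

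- A reader might infer that the mITT set itself can shrink. It cannot: Protocol 9.8 and SAP 7 fix membership by eligibility and attempted treatment.
- A reader might infer that the investigator may end follow-up at will. That reads too much into one item in a list of possible reasons. The reason must be recorded. Protocol 10.3 says that clinical deterioration does not take a subject out, and Protocol 4.0 keeps retreated subjects in safety follow-up. Investigator withdrawal also erases nothing already recorded.
- A reader might set 4.2.1 against the statement in Protocol 4.0 that "All subjects entered will be evaluated, regardless of sequence of treatment that ensues". That sentence concerns the sequence of treatment, and the same section provides for subjects who withdraw consent.
- Removal needs a specific request from the subject, so neither sponsor nor investigator can invoke it. A subject who has died cannot make one, and SAP 10.2 lists deaths apart from discontinuations. The death component is therefore less exposed.
- The goal reversals in step 5 decide nothing now. SAP 6 and 10.4 drop the tests, use exact intervals and say that the intervals are not for inference. The counts 16/150 (10.7%) and 29/150 (19.3%) also lie well above the anticipated maxima of 6% and 14%.
- SAP Table 2 collects adverse events up to the date of early discontinuation, which suggests that events already recorded were meant to count.
- Reasons for discontinuation are tabulated (SAP 10.2), and Protocol 9.9 requires a flow diagram with reasons for exclusion.

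These points narrow the concern without closing it. No text says how a subject whose data are removed is counted or requires such requests to be reported as such. Table 2 governs adverse-event periods and does not override the percentage rule in 10.1 for the primary endpoints.

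**Conclusion.** The point holds in a limited form. A recorded outcome can be lost from the analysed denominator at the subject's request, at any time, with no counting rule. Under the SAP, discontinuation alone can have the same effect on a literal reading. The unqualified investigator item in 4.2.1 does not fit 6.3.8 and 10.3, and the passages must be reconciled.

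What is at stake is the accuracy of the reported RCAO, stroke/death and stenosis rates and their exact intervals, since no formal success decision remains. If subjects with bad outcomes are the ones lost, all three move in the favourable direction. With one such subject lost, the shift is 0.6 to 1.9 percentage points for stenosis, 0.6 to 1.8 for stroke/death and 0.3 to 0.9 for RCAO, over assumed samples of 150 down to 50. These figures assume that the lost subject had the unfavourable outcome. The actual size is unknown and may be zero, because the documents give no count of requests or investigator withdrawals. The change is worth making because it is cheap and the bias cannot be repaired afterwards.

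**What to change.** 1. **Protocol 4.2.1 and SAP 10.6:** state that data recorded up to withdrawal or discontinuation stay in the mITT analysis, and that withdrawal stops further collection only.
2. **SAP 10.1:** state that the wording on early discontinuers does not exclude events already recorded in them, and repeat this under 10.4.1.2 for stroke/death and stenosis.
3. **Where consent already given obliges removal:** keep the subject in the mITT count and report the number and timing of such requests. Show a bound with these subjects as RCAO failures and as safety events. With r such subjects and n others analysed, the bounds are s/(n + r) for RCAO and (x + r)/(n + r) for each safety rate. The consent wording was not available for this check, so simply deleting the exception would be premature.
4. **Protocol 4.2.1 against 6.3.8 and 10.3:** reconcile the investigator-withdrawal item with the two follow-up statements, and report how many entered subjects left for that reason and when.

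The cost is a few sentences in each document and a small amount of extra reporting. The SAP changes remain feasible although the study is closing early. The downside is slightly less favourable rates if removals occurred.
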